3.2 Stage 2: Cohort-Expansion Stage

After a cohort is declared safe and tolerable, cohort-expansion may be instituted for that specific cohort. For a given vemurafenib/ cobimetinib dose and schedule, a minimum of 2 expansion cohorts will be enrolled, and each will consist of approximately 20 patients. Expansion Cohort 1 will be open to patients whose melanoma has progressed while on vemurafenib immediately preceding enrollment in this trial and Expansion Cohort 2 will enroll patients without prior treatment for locally advanced/unresectable or metastatic melanoma or those who are previously treated but without prior exposure to any BRAF or MEK inhibitor therapy. Expansion cohorts will allow for the gathering of additional safety and PK data and the opportunity to better describe the PD effects of the combination. The cobimetinib schedule(s) to be used in each expansion cohort (i.e., 14/14 vs. 21/7 vs. continuous daily schedule) will be based upon an evaluation of safety, activity, and PK results from all patients treated on these schedules during the dose-escalation stage.

Results from the cohort-expansion stage will further inform our choice of the optimal dose and schedule of cobimetinib in combination with vemurafenib for further clinical testing (Table 8).

Table 8 Cohort Expansion for Patients Receiving Vemurafenib and Cobimetinib

Cohort (patient number)	Vemurafenib/Cobimetinib dose, schedule	Eligible patients
1 (n=20)	Combination MTD at one or more dose/schedule	Vemurafenib progressors only
2 (n=20)	Combination MTD at one or more dose/schedule	(PUPs and PTPs)

PTPs: patients previously treated for locally advanced/unresectable or metastatic melanoma but without prior exposure to any BRAF or MEK inhibitor therapy.

PUPs: patients previously untreated for locally advanced/unresectable or metastatic melanoma.

All patients, whether enrolled in the dose-escalation or expansion stage of the study, will be required to provide melanoma tumor biopsy samples at baseline (pre-treatment), Day 14, and at disease progression for PD biomarker analyses. These lesions should have accessible melanoma tumors that may be biopsied with minimal risk and discomfort. In cases where there are no lesions amenable to biopsy, sample collection can be omitted. This should be discussed with the Medical Monitor.

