21. For all patients—previously treated with vemurafenib and those either previously untreated or treated (but without prior exposure to any BRAF or MEK inhibitor therapy) for locally advanced/unresectable or metastatic melanoma—biopsies of accessible tissue are mandatory upon patient’s consent to participate in the trial. Fresh-frozen and paraffin-embedded tumor biopsy for molecular analyses will be obtained within 28 days of Cycle 1, Day 1 (unless progression biopsy tissue was submitted in previous study within 3 months of screening). Biopsies should be completed at least 48 hours before the initiation of study drug therapy on Cycle 1, Day 1. Biopsies (both formalin-fixed and fresh-frozen samples) will be collected at time of progressive disease. A biopsy of tumor tissue must be obtained during Cycle 1 while the patient is receiving cobimetinib; Day 10 to 14 is the required timing for this biopsy. It is highly recommended that the biopsy at disease progression be collected within 3 days after last study treatment. Lesions with the greatest change in dimensional size, based on interval evaluation, are the lesions to be biopsied. Excisional biopsies, punch biopsies, or multiple (2 or more), 14-gauge core needle biopsies are acceptable. **Fine needle aspiration (FNA) biopsies will not be accepted.**
22. For patients who develop any cutaneous lesion(s) suspicious for squamous cell carcinoma (SCC) or keratoacanthoma (KA) during treatment with vemurafenib and/or cobimetinib, biopsy tissue and a paired normal skin biopsy must be obtained for biomarker analyses (mandatory sample). Only one normal skin biopsy is required per patient, regardless of the number of SCC lesions identified and biopsied during the study. Suspicious lesions not thought to represent cutaneous SCC may also be sent for central pathological review at the discretion of the investigator and may undergo molecular characterization.

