5.6.3.1 Tumor Tissue

A final biopsy is requested at the time of progression. A lesion with the greatest change in dimension based on interval evaluation should be excised at time of progressive disease. As stated above, the scheduling of this tumor biopsy should not interfere with the scheduling of the FDG-PET scan.

Tumor biopsies will be obtained from patients with accessible progressing tumors at baseline following the patient's consent to participate in the trial. Failure to obtain

sufficient tumor sample after making best efforts to biopsy the tumor will not be considered a protocol deviation. If a biopsy at progression was submitted to Roche from an antecedent vemurafenib study within 3 months of enrollment, no baseline biopsy is required. For previously untreated patients only, the diagnostic tumor specimen may be substituted as baseline tumor sample.

If archival tumor tissue was not collected during the previous trial, or was inadequate for testing, then archival tumor tissue (formalin-fixed paraffin-embedded archival block or 20 unstained slides) may also be requested. Fine needle aspiration (FNA) biopsies are not acceptable.

In addition to the biopsies noted above, patients will be required to provide tumor biopsies approximately 10–14 days after the start of dosing with vemurafenib and cobimetinib in Cycle 1. The patient must be taking cobimetinib at the time of the Day 10–14 biopsy.

Scheduling of the tumor biopsy should not interfere with the scheduling of the first, post-baseline FDG-PET scan. The FDG-PET scan should not occur within 1 week following a study-mandated biopsy unless the biopsy is obtained from a site that is not a region of interest on the FDG-PET. Ideally, tumor biopsies at screening and during Days 10 to 14 of Cycle 1 should be performed after the mandated PET scans.

See the guidance below regarding the logistics for tumor biopsy and FDG-PET scanning in the case of multiple or single lesions.

- Multiple lesions: The tumor biopsy will be obtained from a lesion other than the one of interest being scanned for FDG-PET and should be obtained 1–4 hours after study drug dosing in Week 2 of Cycle 1, either before or after the scan.

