- Single lesion: For patients with only one lesion for both the FDG-PET and the tumor biopsy, the timing of the FDG-PET scan is more important and the biopsy should be obtained after the second FDG-PET scan. The second FDG-PET scan (performed 10 to 14 days after start of dosing with vemurafenib and cobimetinib in Cycle 1) will be completed first (approximately 1–4 hours after dosing) and the tumor biopsy will then be obtained.

Formalin-fixed tumor tissue embedded in paraffin blocks (FFPE biopsy) and, if feasible, fresh-frozen tumor tissue will be collected at baseline, between Days 10 and 14, and at disease progression. The biopsy at disease progression should be taken from an enlarging lesion. Biopsies at progression should be obtained within 3 days of study drug discontinuation (i.e., continue study treatment for several days beyond documentation of progression, if necessary, in order to coordinate the timing of biopsy to occur within 3 days of study drug discontinuation).

Biopsies will be collected and immediately transferred into provided vials filled with formalin. The biopsies will then be fixed for 24 ± 2 hours, transferred into 70% ethanol, and then (in ethanol) shipped to a central pathology laboratory for paraffin embedding. In cases where a reasonable-sized biopsy (e.g., excisional biopsy, 5-mm punch or more than

one 14-gauge core biopsy) can be collected with formalin fixation, every effort should also be made to collect a fresh-frozen biopsy.

Fresh-frozen tumor (baseline, between Days 10 and 14, and at disease progression) may be used for whole genome analysis; other techniques such as reverse phase protein array or mRNA quantitation may also be performed.

FFPE tumor from baseline and disease progression biopsies will be used to perform the following assessments:

- IHC for molecules known to be relevant for activity of the MAPK pathway (ERK and MEK protein phosphorylation)
- IHC for molecules potentially related to response/resistance including BRAF, CRAF, and PTEN
- BRAF mutations (including V600E) and other somatic mutations affecting PI3K, RAS, RAF, and ERK

The following assessments are planned using the FFPE biopsy taken under treatment (Days 10–14):

- IHC for molecules that are potential PD biomarkers for vemurafenib and cobimetinib (e.g., ERK and MEK phosphorylation).

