A sum of the diameters (longest for non-nodal lesions, short axis for nodal lesions) for all target lesions will be calculated and reported as the baseline sum diameters. If lymph nodes are to be included in the sum, then as noted above, only the short axis is added into the sum. The baseline sum diameters will be used as reference to further characterize any objective tumor regression in the measurable dimension of the disease.

Appendix 1: New Response Evaluation Criteria in Solid Tumors – Version 1.1–Excerpt From Original Publication with Addition of Supplementary Explanations (Eisenhauer et al. 2009) (Cont.)

All other lesions (or sites of disease) including pathological lymph nodes should be identified as non-target lesions and should also be recorded at baseline. Measurements are not required and these lesions should be followed as ‘present’, ‘absent’, or in rare cases ‘unequivocal progression.’ In addition, it is possible to record multiple non-target lesions involving the same organ as a single item on the case report form (e.g. ‘multiple enlarged pelvic lymph nodes’ or ‘multiple liver metastases’).

Response criteria

This section provides the definitions of the criteria used to determine objective tumor response for target lesions.

Evaluation of Target Lesions

Complete Response (CR): Disappearance of all target lesions. Any pathological lymph nodes (whether target or non-target) must have reduction in short axis to <10 mm.

Partial Response (PR): At least a 30% decrease in the sum of diameters of target lesions, taking as reference the baseline sum diameters.

Progressive Disease (PD): At least a 20% increase in the sum of diameters of target lesions, taking as reference the smallest sum on study (this includes the baseline sum if that is the smallest on study). In addition to the relative increase of 20%, the sum must also demonstrate an absolute increase of at least 5 mm. (Note: the appearance of one or more new lesions is also considered progression).

Stable Disease (SD): Neither sufficient shrinkage to qualify for PR nor sufficient increase to qualify for PD, taking as reference the smallest sum diameters while on study.

Special Notes on the Assessment of Target Lesions

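### Early biopsies may excise RECIST target lesions, and the plan does not say how a surgically removed target lesion is scored

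*Combined protocol and SAP*

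**What the plan says.** Table 9, footnote 21 states that "biopsies of accessible tissue are mandatory" for every patient who consents to the trial. For the on-treatment sample, "Day 10 to 14 is the required timing for this biopsy". Section 3.2 gives the exception: "In cases where there are no lesions amenable to biopsy, sample collection can be omitted". The baseline biopsy has substitutes: progression tissue submitted from the previous study within 3 months or, for previously untreated patients, the diagnostic specimen (footnote 21 and Section 5.6.3.1).

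On technique, footnote 21 says: "Excisional biopsies, punch biopsies, or multiple (2 or more), 14-gauge core needle biopsies are acceptable". Section 5.6.3.1 also lists excision among its examples of an adequately sized sample.

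On which lesion to take, Section 5.6.3.1 has two rules. With multiple lesions, "The tumor biopsy will be obtained from a lesion other than the one of interest being scanned for FDG-PET". The second rule begins "For patients with only one lesion for both the FDG-PET and the tumor biopsy" and has that lesion biopsied after the second PET scan, with no bar on excision. Neither rule mentions RECIST target lesions.

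On scoring, Appendix 1 defines complete response in target lesions as "Disappearance of all target lesions", and partial response as a fall of at least 30% in the sum of diameters from baseline. Neither definition restricts the cause. Its text on prior local treatment concerns whether a lesion is measurable at baseline, not removal on study.

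**The concern.** OR, DOR and PFS are all read from the target sum, at least in part. A target lesion that is measured at baseline and then cut out leaves that sum for a reason unrelated to the drugs. For response the error runs in one direction only, upward. The usual safeguards do not help. Confirmation at 4 weeks or more (Section 8.1.2) finds the lesion still absent. Response is investigator-assessed, and central collection of scans is no longer required (Section 5.3.2).

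Superficial lesions of at least 10 mm can be target lesions under Appendix 1, and they are also among the easiest to excise.

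These endpoints are descriptive, but they are used. Section 3.1.4 makes the recommended Phase II dose and schedule depend on safety, activity and PK, and Section 3.2 uses activity in choosing the expansion schedules. Cohorts are small enough for one misclassified patient to show.

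**Working it through.** **Inputs.** There are one to five target lesions, at most two per organ. Partial response (PR) is a fall of at least 30% from the baseline sum. Progressive disease (PD) is a rise of at least 20% and at least 5 mm from the smallest sum on study (all Appendix 1). OR needs confirmation at 4 weeks or more (Section 8.1.2). Expansion cohorts have about 20 patients and escalation cohorts 3–6 (Section 3.1).

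**1. The plan's own figure.** Section 8.3 says that with 20 patients and a true response rate of 20%, the chance of at least one response exceeds 98.8%. Check: 1 − (1 − 0.20)^20 = 0.9885. It reproduces. It assumes that every counted response is a real one.

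**2. Order of events.** Baseline tumor burden is measured within 4 weeks before Cycle 1 Day 1, so the Day 10–14 biopsy always comes later. Sections 3.8 and 5.3.5 place the first response CT/MRI at about Cycle 2 Day 14 ± 7 days. Section 5.3.2 now leaves scan frequency to local standard of care, but no response CT/MRI is scheduled before the Day 10–14 biopsy. An excised target would therefore be in the baseline sum and absent afterwards. A baseline biopsy can also follow the baseline scan, because both have a 28-day window.

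**3. Target sum.** Take k equal targets, excise one, and leave the rest unchanged. The change is −100/k percent. For the remaining lesions to bring the sum to PR they must shrink by s, where (k − 1)(1 − s)/k ≤ 0.70, so s ≥ 1 − 0.70k/(k − 1).

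| k | Change from excision alone | Target-lesion category | Further shrinkage of the rest needed for PR |
|---|---|---|---|
| 1 | −100% | CR | – |
| 2 | −50% | PR | 0% |
| 3 | −33.3% | PR | 0% |
| 4 | −25% | SD | 6.7% |
| 5 | −20% | SD | 12.5% |

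With unequal lesions, excision alone reaches PR only if the removed lesion made up at least 30% of the baseline sum.

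**4. Progression.** Take three 20-mm targets (sum 60 mm), with one excised. If the other two grow to 28 mm each, the sum is 56 mm, a change of (56 − 60)/60 = −6.7%, scored stable. The two remaining lesions have gone from 40 to 56 mm, which is +40%. The 56 mm then becomes the reference for later progression.

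**5. Cohort effect.** One such patient moves the response rate by 1/20 = 5 points in an expansion cohort, and by 1/6 to 1/3 = 17 to 33 points in an escalation cohort. The documents give no frequency, so the following is an assumed range. If a share f of true non-responders were scored as responders, the observed rate would be p + (1 − p)f.

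| True rate p | f | Observed rate | P(at least 1 in 20) |
|---|---|---|---|
| 10% | 0 | 10% | 0.878 |
| 10% | 5% | 14.5% | 0.956 |
| 10% | 10% | 19% | 0.985 |
| 10% | 20% | 28% | 0.999 |
| 0% | 5% | 5% | 0.642 |
| 0% | 10% | 10% | 0.878 |
| 0% | 20% | 20% | 0.988 |

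**The case against.** The strongest reply is that the documents never say an excised lesion counts as response. A reader might infer that Appendix 1 records it as 0 mm. That rule sits under lesions that become too small to measure and concerns a radiologist's judgment of a faint lesion; it does not address surgery. Appendix 1 is silent, and an investigator could call the lesion not evaluable. This stands, and it limits the claim to what a literal reading would produce. It does not remove the problem: the sum is spoiled under either choice, and the choice is left open.

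A reader might also take "Lesions with the greatest change in dimensional size, based on interval evaluation, are the lesions to be biopsied" as steering the Day 10–14 biopsy toward measured lesions. The documents do not support that. The sentence follows the instruction on the progression biopsy, and Section 5.6.3.1 ties the same choice of lesion to progression. No CT/MRI is scheduled between baseline and Day 10–14 that could show a change. Nothing directs the early biopsies to target lesions; they are simply not kept off them.

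A third tempting reading is that a single-lesion patient becomes a complete responder. The rule in Section 5.6.3.1 concerns one lesion that must serve both PET and biopsy, which need not be the patient's only disease. Overall CR also requires no non-target disease and no new lesion.

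Other limits also stand. Excision is one of three accepted techniques. Target lesions are chosen for size, so a small superficial lesion may contribute little to the sum. Failure to obtain enough tissue is not a deviation. The endpoints carry no hypothesis test. Section 18 says that a study report has already been written, so new biopsy wording may reach few patients. The scoring rule can still apply to the final analysis in Section 8.2.1. Section 5.6 puts specimen dates on the eCRF, so a target lesion that vanishes after a biopsy can be queried.

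**Conclusion.** The point holds as a gap in the design with a definite direction and an unknown frequency. The plan requires early biopsies of accessible tumor, accepts excision, spares only the PET lesion, and has no rule for a target lesion removed by surgery. Under a literal reading of Appendix 1, excising 1 of 2 or 1 of 3 equal targets after the baseline scan would by itself give a confirmable PR. With 4 or 5 equal targets it would not, but the rest would need to shrink by only 6.7% or 12.5%. CR would follow only if the sole target were removed and there were no non-target disease or new lesions.

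These figures assume equal lesions, one excision and no drug effect. The cohort effects in step 5 are per hypothetical patient or rest on an assumed frequency. OR, DOR and PFS are affected; DLT and MTD decisions are not. This is a worthwhile low-cost improvement, not a fault in the primary objective.

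**What to change.** In Table 9, footnote 21, and in Section 5.6.3.1, state that Day 10–14 biopsies, and baseline biopsies taken after the baseline scan, should come from a non-target lesion when one is accessible. State also that a RECIST target lesion should not be excised before progression; if only a target lesion is accessible, use punch or core.

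In Section 5.3.2, state that absence of a target lesion due to excision does not count toward CR or PR. Flag the lesion as not evaluable from the biopsy date, with progression still callable from the remaining lesions or new lesions. This fits Appendix 1, which already has a not-evaluable category and allows progression to be called when a lesion measurement is missing.

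The cost is a few sentences and one programming flag. Some biopsies will yield less tissue, and a few patients will become not evaluable for response.

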5.1 Screening Examination and Eligibility Screening Form

All patients must provide written informed consent before any study-specific assessments or procedures are performed.

A pre-screening log needs to be completed and sent to the study leader or Medical Monitor for attribution of the slot.

An Eligibility Screening Form documenting the investigator's assessment of each screened patient with regard to the protocol's inclusion and exclusion criteria is to be completed by the investigator.

A screen failure log must be maintained by the investigator.

A screening examination should be performed between Day -28 and Day -1, except for ophthalmologic examination. The ophthalmologic examination may be performed up to 42 days prior to starting study treatment. Patients who meet all the inclusion and exclusion criteria will be enrolled into the study treatment phase. All screening and baseline assessments are outlined in the Schedule of Assessments, [Table 9](#).

For patients previously treated with vemurafenib, examinations and biopsies performed during the previous study of vemurafenib in which the patient was enrolled may be substituted for screening examinations and biopsies in this study, provided they were performed within 3 months of screening for the current study (see Section [5.3.1](#)).

5.2 Procedures for Enrollment of Eligible Patients

All screening evaluations must be completed and reviewed to confirm that patients meet all eligibility criteria before the first dose of study treatment. Written informed consent for participation in the study must be obtained before performing any study-specific screening tests or evaluations. Informed Consent Forms for patients who are not subsequently enrolled will be maintained at the study site.

All patients at all participating sites will be registered with the Sponsor/designee. Investigators will submit an Enrollment Form and the fully executed Eligibility Screening Form to the Sponsor/designee. The Principal Investigator will be notified of the enrollment/cohort assignment upon receipt. Assignment of a patient number and treatment doses for vemurafenib and cobimetinib will be generated and provided back to the investigator at the time of patient registration.

Under no circumstance will patients who enroll in this study and have completed treatment as specified be permitted to re-enroll in the study with the exception of patients allowed to receive single-agent cobimetinib (after having failed the combination of vemurafenib and cobimetinib, with the Medical Monitor's permission. Such patients are not required to undergo a second screening evaluation prior to initiation of cobimetinib monotherapy.

Results of standard-of-care tests or examinations performed prior to obtaining informed consent and within the screening window may be used; such tests do not need to be repeated for screening. Screening local laboratory assessments performed ≤ 96 hours prior to Day 1 do not have to be repeated.

A patient Enrollment and Identification Code List must be maintained by the investigator.

5.3 Clinical Assessments and Procedures

All patients will be closely monitored for safety and tolerability during all cycles of therapy, at the study completion visit, and during the survival follow-up period. After signing the informed consent, adverse events will be collected as detailed in Section 7.2.1. Patients will be assessed for adverse events weekly during the first two cycles, prior to each subsequent cycle, and as necessary throughout the study. All adverse events will be recorded until 28 days after the last dose of study treatment or until initiation of another anti-cancer therapy, whichever occurs first. Dosing will occur only if the clinical assessment and local laboratory test values are acceptable.

Visits are based on the 28-day cycle. If the timing of a protocol-mandated procedure coincides with a holiday and/or other scheduling conflict that precludes the visit, the visit should be scheduled on the date nearest to the date in question, which may be earlier or later.

